## 10.0 Procedures Involved

*10.1 Provide a description of all research procedures or activities being performed and when they are performed once a subject is screened and determined to be eligible. Provide as much detail as possible.*

*NOTE: This should serve as a blueprint for your study and include enough detail so that another investigator could pick up your protocol and replicate the research. For studies that have multiple or complex visits or procedures, consider the addition of a schedule of events table in in your response.*

Response:

Interested participants will contact the researcher by phone or email and be emailed the screening form and return it to our clinic in person, by mail, or through the REDCap system. They will be notified of their enrollment at least two weeks prior to the beginning of the study.

Following screening, eligible participants will be contacted by mail or email with information regarding the one-time meeting at UB. For subjects participating exclusively online, this session will be video recorded and posted to be viewed prior to the start of the intervention.

At this meeting they will learn about the study, acknowledge their ability to utilize either a smart device or computer to report their meditation times, participate in an educational session, and sign consent forms. Online consent will be obtained through REDCap by a form. Following consent, subjects will be asked to complete the first round of surveys and questionnaires which will include:

- Tinnitus Handicap Questionnaire
- Tinnitus Handicap Inventory
- Tinnitus Functional Index
- Hospital Anxiety and Depression Scale
- Mindful Attention Awareness Scale
- University at Buffalo Tinnitus Intake Questionnaire

← **Formatted:** Bulleted + Level: 1 + Aligned at: 0.75" + Indent at: 1"

Subjects will begin their meditation practice at home using suggested guided meditations. Subjects will be asked to create an account on the meditation website InsightTimer. This website has an accompanying smart device application that allows users to access guided meditations and timed sessions. With an account, users' session data is logged. Subjects will be encouraged to use guided meditations of their choice or timed meditation using the InsightTimer. They will be asked to practice a half hour, five days per week for eight weeks. Subjects must complete at least one hour per week to remain in the study. Every week during the study, subjects will be asked to submit their data from the application into REDCap. Subjects will have the PI's email and a phone number for technical assistance.

Subjects' meditation practice will last for eight weeks with measures being utilized after week three and week eight. The following measures will be sent to participants by email and submitted through REDCap.

- Tinnitus Handicap Questionnaire
- Tinnitus Handicap Inventory
- Tinnitus Functional Index
- Hospital Anxiety and Depression Scale
- Mindful Attention Awareness Scale

← **Commented [RJ25]:** What technology is needed?

**Commented [RJ26]:** What application? Please describe the requirement here in further detail.

**Commented [BF27R26]:** I hope this is clearer now.

← **Formatted:** Bulleted + Level: 1 + Aligned at: 0.75" + Indent at: 1"

**Commented [RJ28]:** You describe above participation for 3 weeks. Are there additional research procedures or activities that are required up to 8 weeks?

**Commented [BF29R28]:** My language was unclear. The intervention lasts 8 weeks with measures after weeks 3 and 8.

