R: This study will ask that you attend a brief meeting on [INSERT DATE AND TIME] or view a video of the session, whichever you would like. In that session, you will learn how to meditate and use the app that we will use to track your meditation. After the information session, I'll ask you to meditate a half hour per day, five days per week, for eight weeks or at the very least, one hour per week. You will be asked to fill out surveys online and submit your data from the app. While the app is free, you will need to use Wi-Fi or data on your smart device or tablet that can run the application. You would be responsible for any charges for data or Wi-Fi.

Do you have any questions about the study or how this might work?

Are you interested in participating in the study?

- [if yes] I would like to take down your email and send you our eligibility screening form. Can I have that?
- [email will be sent using secure, UB email; prospective participant will be sent the appropriate link to the REDCap Screener]
- [if no] Thank you for your time and consideration.

R: I will send a link to that email that will bring you to the screening form. After you fill that out, someone will contact you if you have been selected the study within two weeks. This will not automatically enroll you. You will sign a consent form before the study begins with more details about the study. If you have questions, please contact me at this number [contact] or email [contact].

Recruitment materials and letters are attached.

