## 11.0 Study Timelines

11.1 *Describe the anticipated duration needed to enroll all study subjects.*

Response: Recruitment, screening and enrollment will take no more than two months.

**Commented [31]:** ATTACH Gant chart

**Commented [32R31]:** [https://docs.google.com/spreadsheets/d/14xirM\\_wiNqISiwlwV6XbiPVP1pR3fExYkp2nOtwEQ/edit?usp=sharing](https://docs.google.com/spreadsheets/d/14xirM_wiNqISiwlwV6XbiPVP1pR3fExYkp2nOtwEQ/edit?usp=sharing)

11.2 *Describe the duration of an individual subject's participation in the study. Include length of study visits, and overall study follow-up time.*

Response: Subjects will participate in the study for a total of eight weeks. After providing consent, subjects will participate in an informational session at the UB Speech Language and Hearing Clinic lasting an hour and a half. Online participants will view a video recording of this informational session before the start of the intervention.

**Commented [RJ33]:** 8 or 10 weeks?

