## 26.0 Consent Process

26.1 Indicate whether you will be obtaining consent.

*NOTE: This does not refer to consent documentation, but rather whether you will be obtaining permission from subjects to participate in a research study. Consent documentation is addressed in Section 27.0.*

**Yes** (If yes, Provide responses to each question in this Section)  
 **No** (If no, Skip to Section 27.0)

26.2 *Describe where the consent process will take place. Include steps to maximize subjects' privacy.*

Response: All subjects will be directed to consent materials online through REDCap.

Commented [RJ52]: Please respond to this section.

26.3 *Describe how you will ensure that subjects are provided with a sufficient period of time to consider taking part in the research study.*

*NOTE: It is always a requirement that a prospective subject is given sufficient time to have their questions answered and consider their participation. See "SOP: Informed Consent Process for Research (HRP-090)" Sections 5.5 and 5.6.*

Response: Subjects will be sent consent links through REDCap immediately after eligibility is confirmed. Subjects will have at least one week before the informational meeting to review this consent and ask questions as needed by phone or email.

26.4 *Describe any process to ensure ongoing consent, defined as a subject's willingness to continue participation for the duration of the research study.*

Response: N/A

26.5 *Indicate whether you will be following "SOP: Informed Consent Process for Research (HRP-090)." If not, or if there are any exceptions or additional details to what is covered in the SOP, describe:*

- *The role of the individuals listed in the application who are involved in the consent process*
- *The time that will be devoted to the consent discussion*
- *Steps that will be taken to minimize the possibility of coercion or undue influence*
- *Steps that will be taken to ensure the subjects' understanding*

Response:

We have reviewed and will be following "SOP: Informed Consent Process for Research (HRP-090)."

Commented [BF53]: Will be done via REDCap

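### The baseline questionnaires have no fixed place relative to the meditation instruction, because section 10.1 conflicts with 11.2, 26.2 and 28.1 on when and how consent is given

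*Protocol*

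**What the plan says.** **Section 10.1 (procedures).** At the one in-person meeting, subjects hear about the study, confirm that they can use a device, and then "participate in an educational session, and sign consent forms". The next steps are "Online consent will be obtained through REDCap by a form" and "Following consent, subjects will be asked to complete the first round of surveys and questionnaires". Subjects who take part only online watch a recording of the session at some point ahead of the intervention.

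**Section 10.2 (data collected).** The first battery falls before week 1, with no mention of the session or the video.

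**Section 11.2 (timelines).** "After providing consent, subjects will participate in an informational session". The session lasts an hour and a half. Online subjects see the recording before the intervention starts.

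**Sections 26.2, 26.3 and 28.1 (consent).** "All subjects will be directed to consent materials online through REDCap". On timing, "Subjects will be sent consent links through REDCap immediately after eligibility is confirmed", and "Subjects will have at least one week before the informational meeting to review this consent". Section 28.1 repeats both the REDCap route and the review period.

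**Section 9.3 (telephone script).** Callers are told: "In that session, you will learn how to meditate and use the app". The script lets them choose between attending and watching the video.

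**The concern.** The study has one group and no control. Section 2.1 describes the outcome as reduction in bother before, during and after the eight weeks, so every result rests on the first score. The session is more than administrative, since it includes instruction in how to meditate. The battery consists of self-report scales: three for tinnitus, one for anxiety and depression, and one for mindful attention. These could plausibly respond to teaching or to raised expectations.

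If the first score is taken after the teaching, the measured change leaves out whatever the teaching did. If one mode is measured before the teaching and the other after it, the two sets of change scores do not mean the same thing. Because subjects choose their mode, such an offset would also be mixed up with who chose which. This is a matter of the order of data collection. An analysis plan cannot restore a pre-session score that was never collected.

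**Working it through.** The protocol gives no figure to reproduce: section 17.2 answers the power question as not applicable. The check is therefore a comparison of the sections, followed by an illustration under stated assumptions.

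**1. The sections side by side**

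| Source | Where consent is given | Consent relative to session | Baseline relative to session |
|---|---|---|---|
| 10.1, in person | At the meeting | Listed after it | Follows consent, so after the session if the list is a sequence |
| 10.1, online | REDCap | Not stated | Follows consent; video any time before the intervention, so either side |
| 10.2 | – | – | Before week 1 only |
| 11.2 | – | Before it | Not stated |
| 26.2, 26.3, 28.1 | REDCap, all subjects | At least a week to review; giving of consent not dated | Not stated |

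Two things follow.

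- The sections cannot all be followed. Section 10.1 has forms signed at the meeting, against 26.2 and 28.1 on the route. Read in listed order, it also conflicts with 11.2 on the sequence.
- Settling the consent route does not settle baseline. With REDCap consent for everyone and consent before the session, the battery may still be completed at any time from consent to week 1, on either side of the session or video.

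In every reading baseline precedes home practice. The readings differ only on whether it precedes the instruction.

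**2. Illustration: pre-post change**

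Assumptions, none from the protocol: a true change to week 8 of 0.5 SD of the change score, and a session effect of 0.1 to 0.2 SD that occurs before baseline. From the protocol: target enrolment of 30 (5.1) and paired t-tests as a possible analysis (17.1).

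The observable change is 0.5 − 0.1 = 0.4 SD or 0.5 − 0.2 = 0.3 SD. Power of a two-sided 5% paired t-test comes from the noncentral t distribution with 29 degrees of freedom, critical value 2.045 and noncentrality d√30:

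| d | d√30 | Power |
|---|---|---|
| 0.5 | 2.739 | 0.754 |
| 0.4 | 2.191 | 0.563 |
| 0.3 | 1.643 | 0.355 |

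**3. Illustration: correlation with meditation time**

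A shift shared by all subjects adds a constant to every change score, and a correlation does not change when a constant is added. Only an offset between modes matters, and only if the modes also differ in minutes meditated. With p the online share, δ the baseline offset and m the difference in minutes (both in within-mode SDs), and no true association within mode, the induced correlation is

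r = p(1−p)δm / √{[1 + p(1−p)δ²][1 + p(1−p)m²]}.

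Assume p = 0.5, so p(1−p) = 0.25.

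- δ = 0.1, m = 0.5: 0.0125 / √(1.0025 × 1.0625) = 0.012.
- δ = 0.2, m = 1: 0.05 / √(1.01 × 1.25) = 0.044.
- δ = 0.5, m = 1: 0.125 / √(1.0625 × 1.25) = 0.108.

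At the session effect used in step 2 (0.1 to 0.2 SD) the induced correlation stays below 0.05. The value of 0.108 needs a much larger offset.

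**The case against.** The strongest reply is that the harm largely misses the stated hypothesis. Section 1.2 predicts that reduction in bother correlates with time spent meditating, and a baseline shift common to all subjects leaves that correlation untouched. The power loss above belongs to a paired test, which 17.1 says only may be used. One could add that a baseline taken after the teaching isolates the effect of practice, which is a defensible target. This stands as far as it goes. It does not defend leaving the order open: whichever target is meant, baseline should sit at the same point for every subject, and the protocol also describes its outcome as a before-and-after reduction.

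A reader might draw three stronger conclusions that the text does not support.

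- **That consent is given at least a week before the session.** Sections 26.3 and 28.1 give a week to review the form and do not date the consent. The conflict on order rests on 11.2, and the conflict on route on 26.2 and 28.1.
- **That baseline is taken after the intervention has begun.** Sections 10.1 and 11.2 place the session ahead of the intervention, and 10.2 places baseline before week 1. The supported wording is: after instruction, before home practice.
- **That the two modes will certainly be measured at different points.** The order in 10.1 is that of a list, with no explicit statement of time. If 26.2 and 28.1 govern, the difference in consent route goes, although baseline still has no stated place relative to the session or video.

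Two smaller points also stand. The meeting covers study information and device checks, so not all of its 90 minutes need be teaching. A Hospital Anxiety and Depression Scale score may also exist from before the session, because 6.2 excludes on it. The screening form is not shown, so this is uncertain, and it would cover one instrument only.

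**Conclusion.** The point holds in limited form. Section 10.1 conflicts with 11.2 on the order of consent and session, and with 26.2 and 28.1 on the consent route. No section fixes the baseline battery relative to the session or video. Baseline may therefore follow the meditation instruction, and may do so for some subjects and not others.

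The size is unknown. The fall in power from 75% to 56% or 36% depends wholly on the assumed 0.5 SD change and 0.1 to 0.2 SD session effect, and concerns the pre-post comparison only. For the hypothesised correlation the effect is nil if the shift is common. If it differs by mode, the effect is small under the same session effect, and it further assumes an even split of modes that differ by up to 1 SD in minutes, which nothing in the protocol indicates.

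This should be corrected before enrolment, since the remedy is cheap and a missed pre-session score cannot be recovered. It is not a fatal flaw.

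**What to change.** Reconcile 10.1 with 11.2, 26.2 and 28.1, and state one order for in-person and online subjects alike:

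1. consent through REDCap;
2. the full baseline battery in REDCap, time-stamped;
3. the educational session or its video;
4. week 1 of home practice.

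Remove the signing of consent forms from the meeting activities in 10.1. In 10.2, define the first assessment as after consent and before the session or video, in addition to before week 1. Holding back the video link or admission to the meeting until the battery is complete would enforce the order, but it is optional.

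The cost is a few sentences in 10.1, 10.2 and 11.2 and the order of forms in REDCap. It needs no extra visits, staff or subjects.

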**Commented [BF34R33]:**

This study investigates meditation practice over the course of eight weeks. The goal is averaging 30 minutes, five days each week and a requirement of at least one hour per week. Subjects can practice their meditation anywhere, on their own.

**Commented [RJ35]:** At the end of week 2 or at enrollment? This is not indicated in section 10.1.

**Commented [RJ36]:** What is the requirement? Is it 30 minutes a day for 8 weeks?

In addition to the initial information session, subjects will be asked to complete surveys that are emailed to them after the third and eighth weeks of the study and submitted through REDCap. These surveys should take less than 30 minutes to complete each time they are administered. Additionally, subjects will enter their weekly meditation times in REDCap.

11.3 *Describe the estimated duration for the investigators to complete this study (i.e. all data is collected and all analyses have been completed).*

Response: The duration to complete this study will be 10 months.

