## 20.0      Withdrawal of Subjects

**N/A:** This study is not enrolling subjects. This section does not apply.

Commented [RJ48]: Please respond to this section.

20.1 *Describe anticipated circumstances under which subjects may be withdrawn from the research without their consent.*

Response: Subjects may be withdrawn for the following reasons:

- Failure to submit mediation data in a timely manner.
- Failure to complete surveys and questionnaires in a timely manner.
- Failure to comply to participating in the intervention. Subjects practicing meditation less than one hour per week may be withdrawn from the study.

20.2 *Describe any procedures for orderly termination.*

*NOTE: Examples may include return of study drug, exit interview with clinician. Include whether additional follow up is recommended for safety reasons for physical or emotional health.*

Response: Participants will be informed of their removal from the study and asked to complete questionnaires (Tinnitus Handicap Questionnaire, Tinnitus Handicap Inventory, Tinnitus Functional Index, Hospital Anxiety and Depression Scale, Mindful Attention Awareness Scale) via the REDCap system. This intervention poses low risk from discontinuing abruptly.

20.3 *Describe procedures that will be followed when subjects withdraw from the research, including retention of already collected data, and partial withdrawal from procedures with continued data collection, as applicable.*

Response: Data already collected from subjects who withdraw will be analyzed up to the point of their last completed questionnaires.

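### Subjects below one hour of practice a week can be removed without their remaining week-3 and week-8 measures, although minutes meditated are the exposure under test

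*Protocol*

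**What the plan says.** The only hypothesis (protocol 1.2) is a correlation between the drop in bother and the time meditated. The design is non-randomized and describes no comparison group (4.1), so the spread of minutes among subjects carries the test.

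The one-hour floor appears in four places:
- Section 10.1: "Subjects must complete at least one hour per week to remain in the study".
- Section 11.2: "The goal is averaging 30 minutes, five days each week and a requirement of at least one hour per week".
- Section 9.3, phone script: "for eight weeks or at the very least, one hour per week".
- Section 20.1: "Subjects practicing meditation less than one hour per week may be withdrawn from the study".

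Outcomes are taken before week 1, with "measures being utilized after week three and week eight" (10.1, repeated in 10.2). For a removed subject, section 20.2 provides one set at exit: "Participants will be informed of their removal from the study and asked to complete questionnaires". Section 20.3 then states: "Data already collected from subjects who withdraw will be analyzed up to the point of their last completed questionnaires". Section 20.1 has a separate ground for withdrawal that is not tied to minutes: "Failure to complete surveys and questionnaires in a timely manner".

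**The concern.** Eligibility to stay under measurement depends on the variable whose effect is being estimated. Three things follow.

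1. The sections do not agree on whether removal is automatic (*must*, *requirement*) or discretionary (*may*). None defines the trigger: one low week, repeated low weeks, or an average.
2. After removal nothing provides the week-8 questionnaires, or the week-3 set if removal comes earlier. These gaps fall at the low end of the exposure range, which a dose-response analysis most needs.
3. The exit set does not replace the week-8 score. It is taken at a time fixed by low practice itself, so few cumulative minutes go with short follow-up. Improvement that merely accrues with time can then look like an effect of minutes.

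A later analysis plan can model timing and missingness, but it cannot restore a week-8 score that was never requested.

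**Working it through.** **Inputs from the protocol.** Requested practice is 30 min × 5 days = 150 min/week (10.1). The floor is 60 min/week (10.1, 11.2, 20.1). Target enrolment is 30 (5.1). Follow-up scores come after weeks 3 and 8 (10.1, 10.2). The power analysis is answered as not applicable (17.2), so the plan has no figure of its own to reproduce.

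**Assumptions (none is in the protocol).** Two-sided 0.05; true r = 0.5; mean week-8 change δ = 0.5 SD. Person-mean minutes follow a gamma distribution with (A) mean 110, SD 50 or (B) mean 130, SD 35. Weekly minutes are the person mean times a lognormal factor with CV 0.30. The trigger is read three ways: (i) first week below 60; (ii) second such week; (iii) running mean below 60 from week 3. Exit in weeks 1–7 counts as removal, and a subject removed at week 3 or later holds a week-3 score.

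**Model.** Week-8 change = δ + r·z(mean minutes over 8 weeks) + e, with e ~ N(0, 1 − r²). Change at week t = f(t)·[δ + r·z(mean minutes so far)] + e, with f(t) = t/8 (linear) or (1 − exp(−t/2))/(1 − exp(−4)) (early plateau). The test is a Pearson correlation with cumulative minutes up to the score used, in 20,000 simulated trials of 30 subjects.

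**Anchor.** The Fisher-z formula gives Φ(atanh(0.5)·√27 − 1.96) = Φ(0.549 × 5.196 − 1.96) = Φ(0.89) = 0.81. The simulated value in (A) with everyone followed is 0.812.

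**Removal and power, linear change (order i / ii / iii).**

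| | (A) 110, SD 50 | (B) 130, SD 35 |
|---|---|---|
| Removed | 43 / 30 / 19% | 18 / 7 / 2% |
| All followed to week 8 | 0.81 | 0.82 |
| All exit forms used, timing ignored | 0.80 / 0.78 / 0.78 | 0.73 / 0.78 / 0.80 |
| All exit forms used, adjusted for exit week | 0.47 / 0.58 / 0.65 | 0.67 / 0.75 / 0.79 |
| No exit forms, week-3 scores kept | 0.60 / 0.70 / 0.78 | 0.68 / 0.75 / 0.79 |
| Removed subjects dropped (20.3 does not say this) | 0.45 / 0.54 / 0.64 | 0.66 / 0.74 / 0.79 |

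In (A), removal before week 3 affects 27.8 / 12.4 / 0% of subjects. Without exit forms, 30 × (1 − 0.278) = 21.7, 30 × (1 − 0.124) = 26.3 and 30 subjects contribute a follow-up score. Their mean change is 0.66 / 0.58 / 0.51 SD against a true 0.50, so a paired pre-post comparison (17.1) is also flattered.

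**False-positive rate with no effect of minutes (r = 0), all exit scores used, timing ignored (order i / ii / iii).**

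| | δ = 0.5 SD | δ = 1.0 SD |
|---|---|---|
| (A) linear | 13.5 / 8.9 / 7.3% | 38.2 / 20.7 / 14.1% |
| (A) plateau | 7.8 / 5.6 / 5.2% | 16.5 / 7.4 / 5.9% |
| (B) linear | 8.3 / 5.4 / 5.2% | 17.9 / 7.2 / 5.7% |

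With full follow-up the rate is 4.9–5.0%. Regression on mean minutes plus exit week gives 4.7–5.1%.

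The power near 0.80 in (A) with all exit forms is therefore less reassuring than it looks: the same analysis rejects 7–14% of the time when minutes do nothing. Once timing is adjusted for, power is 0.47–0.65.

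**Sensitivity to the practice distribution.** A simpler calculation used normally distributed minutes (mean 100–150, between-subject SD 40–60, weekly SD 0 or 30) and dropped removed subjects altogether. At r = 0.5, removal on an average below 60 keeps 75–99% of subjects, with power 0.47–0.78. Removal on any single week below 60 (weekly SD 30) keeps 48–86%, with power 0.24–0.60. Dropping overstates the loss, because 20.2 and 20.3 retain some data.

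**The case against.** **The wording can be reconciled as it stands.** A participation requirement enforced at the investigator's discretion is coherent, and the phone script names the same floor. The script's silence on removal shows little, because it refers the caller to a consent form that is not in the material reviewed. This has force, but it leaves the trigger undefined and does not settle whether removal is automatic.

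**The protocol already limits the loss.** All five follow-up instruments are requested at removal, earlier data are kept, and a subject removed at week 3 or later may hold a scheduled week-3 score. This stands: outcomes are not wholly lost. What is missing is the week-8 score, and the week-3 score for early removals.

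**The size rests on assumptions.** This also stands. The 38% figure needs the strictest trigger, 43% of subjects removed, linear improvement to 1.0 SD, cumulative minutes as the exposure and no allowance for time. With mean weekly minutes as the exposure it is about 30%; with an early plateau it is about 17%.

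**The inflated error belongs to the analysis plan.** This is partly right, since adjusting for exit week restores 5%. But adjustment costs power, because the rule ties exit week to minutes, and it cannot supply scores that were never collected.

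**An adherence floor is a legitimate choice for a small unfunded study.** Agreed. The point concerns measurement after the floor is crossed, not the floor.

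**Conclusion.** The concern holds. As written, scheduled outcomes are lost according to the exposure in the hypothesis, and only a change to data collection in the protocol prevents it. The size cannot be fixed, because the protocol gives no trigger, practice distribution, use of discretion or exit response. On the assumed inputs the result runs from negligible (B with a running-mean trigger: 2% removed, power 0.79–0.80 against 0.82) to substantial (A with removal at the first low week: 43% removed, power 0.60 without exit forms or 0.47 with exit forms adjusted for timing, against 0.81). The false-positive rate rises above 5% only if exit scores are analysed without regard to timing. This should be fixed before enrolment, with medium confidence in its practical size.

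**What to change.** 1. Reconcile 10.1, 11.2, 20.1 and the phone script in 9.3, and state what triggers removal and whether it is automatic. Which practice rule applies is for the investigator.
2. In 10.1 and 20.1–20.3, separate stopping practice from stopping data collection. Keep sending the weekly minutes form and the week-3 and week-8 questionnaires to every enrolled subject who has not withdrawn consent, whatever minutes are logged.
3. Keep these subjects in the exposure-response analysis with their actual minutes.
4. Record the date of any exit questionnaire so that it is not taken for a week-3 or week-8 score.
5. As a secondary point, accept late forms with their actual date instead of ending data collection for lateness. The case does not depend on this.

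The cost is protocol wording and a few more automated REDCap emails. Mean practice time and mean improvement may look slightly less favourable, because low practisers stay in the averages.
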